12 STATISTICAL CONSIDERATIONS

12.1 Study Hypotheses

This study examines the effect of a bundled “best practices” intervention that includes locally tailored dietary and oral health education provided during pregnancy and the postnatal period; 2) oral health care of children including the application of fluoride varnish; 3) motivational interviewing with children’s mothers; and 4) patient navigation of existing oral health and other social services in each study community, facilitated by CHRs. This treatment will be compared to a healthy lifestyle intervention which includes maternal and child health, child developmental milestones, nutrition and other healthy behavior.

Primary outcome

Number of decayed, missing or filled primary tooth surfaces – dmfs – at the last oral assessment

The hypothesis for the primary outcome dmfs is that a bundled “best practices” oral health and fluoride varnish intervention will reduce early childhood caries relative to a healthy lifestyle intervention comparison group.

Ho: mean oral health group dmfs = mean healthy lifestyle group dmfs

Ha: mean oral health group dmfs \neq mean healthy lifestyle group dmfs

If this hypothesis is confirmed we will then calculate the prevented fraction which “...is the difference in mean caries increments between the treatment and control groups expressed as a percentage of the mean increment in the control group” (Marinho et al. 2013, p. 1). This will be a descriptive supplement to the primary endpoint analysis rather than a separate statistical hypothesis test. We do not plan to analyze twelve month dmfs data but will incorporate 12 month assessments in models to multiply impute missing dmfs scores for the last assessment.

Secondary endpoints

Average number of decayed, missing or filled teeth at the last oral assessment (dmft; excluding non-cavitated lesions)

Hypothesis: average dmft will be lower in the oral health group

Ho: oral health group average dmft = healthy lifestyle group average dmft

Ha: oral health group average dmft \neq healthy lifestyle group average dmft

Mother/caregiver oral health knowledge at Visit 6

Hypothesis: caregiver oral health knowledge will be higher in the oral health group

Ho: mean oral health group oral health knowledge = mean healthy lifestyle group oral health knowledge

Ha: mean oral health group oral health knowledge \neq mean healthy lifestyle group oral health knowledge

Mother/caregiver oral health behavior at Visit 6

Hypothesis: caregiver oral health behavior will be higher in the oral health group
Ho: mean oral health group oral health behavior = mean healthy lifestyle group oral health behavior
Ha: mean oral health group oral health behavior \neq mean healthy lifestyle group oral health behavior

Caregiver attitudes towards oral health care at Visit 6

Hypothesis: caregiver oral health attitudes will be higher in the oral health group
Ho: mean oral health group attitudes = mean healthy group lifestyle attitudes
Ha: mean oral health group attitudes \neq mean healthy lifestyle group attitudes

Maternal/child health knowledge at Visit 6

Hypothesis: caregiver maternal/child health knowledge will be higher in healthy lifestyle group
Ho: mean oral health group maternal/child knowledge = mean healthy lifestyle group maternal/child knowledge
Ha: mean oral health group maternal/child knowledge \neq mean healthy lifestyle group maternal/child knowledge

12.2 Sample Size Considerations

A Cochrane meta-analytic review⁹ estimated that fluoride varnish reduces the prevalence of decayed, missing and filled first teeth surfaces (dmfs) by 37%. An Indian Health Services survey reported a mean dmfs in 2-year olds of 10.05 (standard deviation [SD]=16.27).¹⁴ A 37% reduction from this low base rate would require prohibitively large samples from these communities. To increase sensitivity and efficiency we will follow our sample from a minimum of 2 years and some children to a maximum of 3 years of age. Recent data from 3-year olds on the Navajo Nation showed a mean dmfs of 18.2 (SD=19.4). Therefore, for sample size calculations, we estimate values halfway between ages 2 and 3, i.e., mean dmfs=14 (SD=17.25). Using Stata 15.1 (StataCorp, College Station, TX) with power = 0.80, alpha = 0.05 (two tailed) for an independent *t*-test a sample of 352 is necessary to detect a 37% reduction in caries experience (dmfs of 14 vs 8.8; SD=17.25). To cover the estimated 19% attrition rate reported in the Cochrane review would require 434 participants. This is the theoretical maximum sample size necessary in this context. However, sample size estimates are highly sensitive to the estimated variability of dmfs measurements. A 35% reduction in the standard deviation (SD=11.2) for the same effect size would require only 150 participants for power = 0.80 (N=185 to cover attrition). Prior studies in AI groups have not evaluated fluoride varnish application in combination with prenatal maternal intervention using MI techniques and care coordination. This novel and intensive treatment combination should produce a larger effect than varnish alone and also reduce extreme caries experience, i.e., reduce dmfs variability. Our statistical sensitivity is also enhanced by following early enrollees up to an average expected age of ~ 2.5 years. Our recruitment timeline targets enrollment of 350 pregnant women across both sites. With 19% attrition we would retain an effective sample size of 283.5. To be

conservative we round down to an even number of 282 (141 per group) which provides power of 0.71 for a 2-tailed test with alpha .05 and a 37% treatment group difference in dmfs. This sample size achieves power = 0.97 under the smaller standard deviation assumption. Current standards of care recommend FV application for all children at high risk for caries. Study staff will therefore apply FV to children in the Healthy Lifestyle group at 12 and 24 months of age. This will potentially dilute between groups caries differences but is a necessary accommodation given the high caries burden in AI communities.

We feel this is a statistically defensible target enrollment given the high fluoride varnish application frequency in our study and the ~ 2.5 years of follow-up time from birth. Moreover, genuine treatment effects occurring below our statistical detection threshold or within highly variable decay experiences are unlikely to be clinically and ecologically relevant. Both calculations are based upon the average effects of fluoride varnish alone⁹ and thus should be conservative. In this regard an Australian trial that enrolled expectant Aboriginal women suggests the combination of MI and fluoride varnish results in a larger treatment effect than varnish alone³ and that this difference persisted over 5 years of follow up.¹⁵ Power analysis based upon their data is presented in the section below.

On average 9 and 23 women per month give birth at Hopi and Crow, respectively. We target recruiting 7 per month at Hopi and 18 per month at Crow. This will achieve our target enrollment by 14 months and will accrue a larger number of participants at Crow (N=252) than Hopi (N=98). Our study is not designed to compare intervention effectiveness across tribes but rather across treatment groups. Therefore, the enrollment imbalance across sites does not affect our primary research question as both groups will be combined when evaluating all outcomes.

Secondary outcome power analysis

Secondary outcomes include a complementary caries measure and a set of caregiver-assessed health knowledge and behavior domains.

Average number of teeth with decay. The secondary oral health outcome measure is the average number of decayed, missing or filled teeth (dmft) as defined by cavitated lesions (or worse). We count only cavitated lesions because this threshold is used in other AI studies^{1,2} and because of low examiner reliability for identifying noncavitated lesions.¹⁶ Treatment with three fluoride varnish applications and motivational interviewing produced an average difference of -0.19 teeth with cavitated lesions (95% CI -0.23, -0.16) among 2-year old children.³ Because the variability of this measure is substantially lower (SD=0.22), statistical power to detect this treatment difference with 100 per group using an independent *t*-test exceeds 0.99 with alpha = 0.05 two-tailed. Doubling this variability estimate (SD=0.44) provides power of 0.86 with 100 per group. Another approach is to calculate power using the lower 95% confidence limit for the treatment group difference in Jameison et al. That difference estimate (-0.16) provides power > 0.99 with 100 per group. If no missing or filled teeth are observed (as was the case in Jamieson) we will analyze the outcome as dt.

Oral health knowledge. With a sample size of 282 this study has power of 0.81 to detect a 15% difference in post-test knowledge scores across the treatment groups (e.g., 65% vs. 80% correct).

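### Section 12.2: the planning SD of 17.25 is not the halfway value it is said to be (17.84), so the printed sample size and power do not follow from the plan's own rule

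*Combined protocol and SAP*

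**What the plan says.** All of this is in Section 12.2, Sample Size Considerations.

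- For age 2, a survey "reported a mean dmfs in 2-year olds of 10.05 (standard deviation [SD]=16.27".
- For age 3, recent data from "3-year olds on the Navajo Nation showed a mean dmfs of 18.2 (SD=19.4".
- The planning values are then fixed: "we estimate values halfway between ages 2 and 3, i.e., mean dmfs=14 (SD=17.25".
- From these, for an independent t-test with 80% power and two-sided alpha 0.05, "a sample of 352 is necessary to detect a 37% reduction in caries experience". The section writes the two means as 14 and 8.8.
- Allowing for losses: "To cover the estimated 19% attrition rate reported in the Cochrane review would require 434 participants".
- On that last figure: "This is the theoretical maximum sample size necessary in this context".
- As a more favourable case: "A 35% reduction in the standard deviation (SD=11.2) for the same effect size would require only 150 participants", or 185 with attrition.
- Enrolment is set at 350. After 19% attrition the plan counts on 282 children (141 per group) and reports power of 0.71, or 0.97 with the smaller SD.

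**The concern.** The section gives an explicit rule for its inputs, and one of the two inputs does not obey it. The halfway mean of 14.125 is fairly rounded to 14, but 17.25 is too far from the midpoint of the two SDs to be rounding. The required sample size grows with the square of the SD, so the error carries into every figure in the main scenario: the total, the attrition-adjusted total and the power at 282. These are the power statement for the primary outcome, and a reader who applies the stated rule cannot reproduce them. The sentence calling 434 a maximum adds to the problem, because it presents as a ceiling a figure that the rule itself exceeds.

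**Working it through.** **Inputs (Section 12.2).** Age 2: mean 10.05, SD 16.27. Age 3: mean 18.2, SD 19.4. Reduction 37%, two-sided alpha 0.05, power 0.80, attrition 19%, 141 analysed per group. Allocation is 1:1 (Section 5.4).

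**Method.** Two-sample t-test with the noncentral t distribution. For n per group, the noncentrality is difference / (SD × √(2/n)) with 2n − 2 degrees of freedom. The attrition-adjusted total is N / 0.81.

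**Step 1: reproduce the plan.** Difference = 0.37 × 14 = 5.18, SD 17.25.
- N = 352.
- 352 / 0.81 = 434.6, which the plan prints as 434.
- At n = 141 the noncentrality is 5.18 / (17.25 × √(2/141)) = 2.52, giving power 0.710.
- With SD 11.2, N = 150, 150 / 0.81 = 185.2 and power is 0.972.

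All printed figures are confirmed, so the fault lies in the SD input alone.

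**Step 2: apply the stated rule.**
- Mean: (10.05 + 18.2) / 2 = 14.125, consistent with 14.
- SD: (16.27 + 19.4) / 2 = 17.835, i.e. 17.84.

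Other ways of combining the two SDs do not give 17.25 either: harmonic mean 17.70, geometric mean 17.77, root mean square 17.90, and a half-and-half mixture that includes the difference between the age means 18.36. The printed SD lies (17.25 − 16.27) / (19.4 − 16.27) = 31% of the way from age 2 to age 3. The printed mean lies (14 − 10.05) / (18.2 − 10.05) = 48% of the way.

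**Step 3: recompute with SD 17.835.**

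| Difference used | N | N / 0.81 | Rounded up | Power, 141 per group |
|---|---|---|---|---|
| 37% of 14 = 5.18 | 376 | 464.2 | 465 | 0.681 |
| 14 − 8.8 = 5.2 | 372 | 459.3 | 460 | 0.684 |
| 37% of 14.125 = 5.226 | 368 | 454.3 | 455 | 0.689 |

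The first row matches the inputs that reproduce the plan's 352. Truncated as the plan truncates 434.6, its attrition-adjusted figure is 464. Every row is above 352 and 434, and below 0.71.

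**Step 4: the knock-on for the smaller SD.** 0.65 × 17.25 = 11.21, so 11.2 is a 35% reduction from 17.25. From 17.835, a 35% reduction is 0.65 × 17.835 = 11.59. With difference 5.18 that gives N = 160, 160 / 0.81 = 197.5 (198), and power 0.962.

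**The case against.** Five arguments can be made for the plan.

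1. *The misprint may be elsewhere.* 17.25 would be the exact midpoint if the age-2 SD were 2 × 17.25 − 19.4 = 15.10, or if the age-3 SD were 2 × 17.25 − 16.27 = 18.23. The sources are not available here, so the documents show that the three SDs disagree but not which one is wrong. This stands. The recomputed figures hold only if 16.27 and 19.4 are right.

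2. *The size depends on rounding.* This also stands, and it is why a range is reported. The rule applied strictly to both inputs gives the mildest result (368, 455, 0.689).

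3. *The maximum is claimed only for this context, meaning the halfway scenario.* That reading is fair, but it does not save the sentence, because the halfway scenario itself needs 455 to 465.

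4. *The primary model adjusts for age, sex and site (Section 12.4), so the residual SD may be smaller.* Covariates explaining 1 − (17.25 / 17.835)² = about 6.5% of the variance would bring 17.835 down to 17.25. That is possible. But the plan gives no proportion of variance explained, specifies an unadjusted t-test for sizing, and does not derive 17.25 this way.

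5. *No decision changes.* Correct. Enrolment follows the recruitment timeline, and power below 0.80 is already disclosed.

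A reader might also infer more than the documents support:

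- *That the trial needs 746 participants.* The age-2 values do give N = 604 (difference 0.37 × 10.05 = 3.72, SD 16.27), or 604 / 0.81 = 745.7. But the plan raises that case only to set it aside ("A 37% reduction from this low base rate would require prohibitively large samples from these communities") and extends follow-up instead. It is not this trial's requirement.
- *That the plan's remark about its calculations being conservative is false, or that the smaller SD is improperly presented.* The section discloses that varnish in the comparison arm may dilute the difference, while the oral health arm adds motivational interviewing and care coordination to varnish. The net direction is unknown. The SD of 11.2 is openly labelled an assumption and comes with a rationale.

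**Conclusion.** Wrong as written, with small impact. On the printed source values, the SD used for the primary sample size does not follow the rule given for it. Relative to the plan, the total rises by 16 to 24 (from 352 to 368–376), the attrition-adjusted total by 21 to 31 (from 434 to 455–465), and power at 282 falls by 2 to 3 points (from 0.71 to 0.68–0.69). This assumes that 16.27 and 19.4 are correctly transcribed, that halfway means the simple midpoint, and that the plan's t-test with equal SDs in both arms is kept. The maximum sentence is unsupported on the same basis. The finding does not show that enrolment must rise or that the planned analysis is unsound.

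**What to change.** Change Section 12.2 only.

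- Check 16.27, 19.4 and 17.25 against their sources. If a source SD proves to be misprinted, correct it and recompute the midpoint and the figures that depend on it.
- If 16.27 and 19.4 stand, replace 17.25 with 17.84 and restate the total as 376 (465 with attrition) and power at 282 as 0.68. Otherwise, give a source for 17.25 and remove the word halfway.
- Delete the sentence that calls the figure a theoretical maximum.
- If 17.84 is adopted, keep the SD 11.2 scenario with 150 (185 with attrition) and power 0.97, but drop its description as a 35% reduction. A true 35% reduction would be 11.59, with 160 (198 with attrition) and power 0.96.

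Keep enrolment at 350 and the analysis as planned. The cost is a text edit and, if 17.84 is adopted, a slightly less favourable power statement. No additional participants are needed.

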However, an Australian clinical trial indicates that the combination of early intervention and fluoride varnish application may be effective in preventing caries among very young children in indigenous settings.³ Jamieson et al. enrolled pregnant aboriginal Australian women.³ The active treatment arm included motivational interviewing for caregivers and fluoride varnish application for children aged 6 to 24 months. This treatment combination resulted in fewer decayed teeth in two year old children compared to a usual care control group (means of 0.62 teeth [95%CI 0.59, 0.65] versus 0.89 [95%CI 0.85, 0.92], respectively).

Together these studies suggest that to prevent caries in indigenous children, interventions should a) start at birth before caries develop; b) utilize behavioral strategies such as motivational interviewing; and c) complement behavioral strategies with fluoride varnish application. The present study will recruit expectant mothers in two AI communities (Hopi and Crow) and utilize both motivational interviewing and multiple fluoride varnish applications (at 6, 12, 18 and 24+ months of age) to reduce ECC. This Oral Health intervention will include prenatal education regarding oral hygiene practices,

oral health screening and referral for children and fluoride varnish application every 6 months. These treatments are provided by community health representatives who incorporate locally and contextually relevant strategies for ECC prevention and use AI community members to implement the intervention. Contextually relevant strategies were identified in a formative assessment of each community prior to clinical trial enrollment.

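### Section 12.2's dmft powers (>0.99, 0.86, >0.99) rest on SDs of 0.22 and 0.44, which the plan's main dmfs assumption (mean 14, SD 17.25) rules out

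*Combined protocol and SAP*

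**What the plan says.** The secondary power paragraph of section 12.2 takes a difference of 0.19 teeth with cavitated lesions (95% CI 0.16 to 0.23 in absolute size), observed in 2-year-olds in the cited Australian trial, and an SD of 0.22. It says: "Because the variability of this measure is substantially lower (SD=0.22), statistical power to detect this treatment difference with 100 per group" exceeds 0.99 with a two-sided t-test at alpha 0.05. Two checks follow: "Doubling this variability estimate (SD=0.44) provides power of 0.86 with 100 per group", and, for the confidence limit nearest zero, "That difference estimate (-0.16) provides power > 0.99 with 100 per group". No source or derivation is given for 0.22.

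Earlier in section 12.2 the primary outcome is planned as follows: "we estimate values halfway between ages 2 and 3, i.e., mean dmfs=14 (SD=17.25"), and the sample is sized to "detect a 37% reduction in caries experience (dmfs of 14 vs 8.8; SD=17.25"). An optimistic alternative is also given: "A 35% reduction in the standard deviation (SD=11.2) for the same effect size would require only 150 participants". The analysed sample is 282, or 141 per group. In justifying the enrolment target, section 12.2 points the reader forward to a power analysis based on the Australian trial's data.

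The dmft score is described in three ways. Section 3.2 counts the teeth whose own dmfs exceeds 1 and sums them per child. Section 8.1 divides the number of decayed teeth by the number of erupted teeth. Section 12.2 counts teeth with cavitated lesions or worse.

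**The concern.** Section 8.1 derives dmft from the dmfs examination, so the two scores describe the same mouths. A population in which affected surfaces vary with an SD of 17.25 cannot have affected teeth that barely vary. An SD of 0.22 teeth looks far too small beside that assumption, and doubling it is not a real stress test if both values are out of reach.

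The stated dmft powers follow a primary power of only 0.71 under the main assumption, and section 12.2 uses the calculation as support for the enrolment target. A reader would take 0.86 to >0.99 as the trial's power on its second caries measure. That reader could then treat a null dmft result as evidence against an effect of 0.19 teeth.

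**Working it through.** **Inputs from the plan.** Difference 0.19 (or 0.16) teeth; SD 0.22 and 0.44; 100 per group (12.2). dmfs mean 14 versus 8.8, SD 17.25, 141 per group (12.2). dmft as a sum of teeth per child (3.2). **Assumption not in the plan:** 20 primary teeth with at most five surfaces each. Powers are by noncentral t, two-sided alpha 0.05.

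**1. The plan's own figures.** At 100 per group: 0.19 with SD 0.22 gives >0.999; 0.19 with SD 0.44 gives 0.860; 0.16 with SD 0.22 gives 0.999. All three reproduce, so only the SD is in question.

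**2. Whole-number floor.** A whole-number variable with mean m has variance of at least f(1 − f), where f is the fractional part of m. For two arms 0.19 apart, the average of the two minimum variances is smallest when one mean is a whole number: (0 + 0.19 × 0.81)/2 = 0.07695, so the pooled SD is at least 0.277. For 0.16: (0.16 × 0.84)/2 = 0.0672, SD at least 0.259. So 0.22 cannot occur together with either difference. By itself this changes little: at SD 0.277 with 100 per group, power is 0.998 for 0.19 and 0.98 for 0.16. The value 0.44 passes this test.

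**3. Floor from the dmfs assumption.** Let S be dmfs and T dmft, with T ≤ S ≤ 5T. Then (S − T)(5T − S) ≥ 0, so E[S²] ≤ 6E[ST] − 5E[T²]. Write M and σ for the mean and SD of S, and s for the SD of T. Bounding the covariance by sσ and maximising over the mean of T (at 0.6M) gives σ² ≤ 0.8M² + 6sσ − 5s².

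- M = 14, σ = 17.25: 5s² − 103.5s + 140.76 ≤ 0, so s ≥ 1.463. A linear programme over whole-number pairs with 20 teeth gives 1.467, at mean dmft about 8.5. Under section 3.2's rule that a tooth counts only above 1, it gives 1.71.
- M = 8.8, σ = 17.25: 5s² − 103.5s + 235.61 ≤ 0, so s ≥ 2.604 (programme 2.61; 2.29 under the section 3.2 rule).
- Pooled over arms: √((1.467² + 2.61²)/2) = 2.12; under the section 3.2 rule √((1.71² + 2.29²)/2) = 2.02.

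Both 0.22 and 0.44 lie below every one of these values. The control-arm floor alone is 1.467/0.22 = 6.7 times the stated SD and 1.467/0.44 = 3.3 times the doubled one.

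**4. Unadjusted power for 0.19 teeth at these SDs**

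| dmft SD | 100 per group | 141 per group |
|---|---|---|
| 0.22 (plan) | >0.99 | >0.99 |
| 0.44 (plan) | 0.86 | 0.95 |
| 1.47 | 0.15 | 0.19 |
| 1.71 | 0.12 | 0.15 |
| 2.12 | 0.10 | 0.12 |

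**5. Source of the effect.** For 2-year-olds, section 12.2 cites a survey that "reported a mean dmfs in 2-year olds of 10.05 (standard deviation [SD]=16.27"). At five surfaces per tooth, that mean needs at least 10.05/5 = 2.01 affected teeth. Section 2.1 gives the Australian trial's decayed teeth as "means of 0.62 teeth [95%CI 0.59, 0.65] versus 0.89 [95%CI 0.85, 0.92], respectively". The 0.19 therefore appears to come from a lower-caries population, though the two tooth measures may not be the same.

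**6. A proportionate effect.** If every affected tooth has all five surfaces affected, mean dmft is 14/5 = 2.8 and SD is 17.25/5 = 3.45. A 37% reduction is then 1.036 teeth, with power 0.71 at 141 per group, as for dmfs. Over all dmft distributions compatible with dmfs mean 14, SD 17.25, power for a 37% reduction runs from about 0.49 (mean 3.96, SD 6.37) to >0.99.

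**The case against.** Several replies have force.

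- **The optimistic SD.** With dmfs SD 11.2 there is no floor on the dmft SD in the control arm at mean 14. This stands, and the conflict is claimed only for the main assumption, which underlies the required sample of 352 and the power of 0.71.
- **Covariates.** Section 12.4 analyses dmft in parallel with dmfs, adjusting for age, sex and site, so the residual SD may fall below the marginal floor and 0.19 is not a ceiling on power. This stands too. For an assumed R-squared of 0.2 to 0.4, the residual SD is 1.467 × √0.8 = 1.31 to 1.467 × √0.6 = 1.14, and power at 141 per group is about 0.23 to 0.29. That is still far from 0.86.
- **The ratio scale.** Under section 8.1, dmft is a proportion of erupted teeth, for which SD 0.22 is possible. The 0.19 effect is in teeth, however, so this definition does not rescue the calculation.
- **Limited consequence.** dmft is secondary, enrolment does not depend on it, and a null result would be read mainly from its confidence interval. This is fair, and it limits the weight of the point.

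A reader might also infer that SD 0.22 is impossible for any tooth count. It is not, since a count with mean near 0.05 could have it; it is impossible only jointly with the stated difference. Nor do the means 0.62 and 0.89 in section 2.1 supply a higher floor. They differ by 0.27, not 0.19, and the documents do not say that they measure the same outcome.

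**Conclusion.** The three dmft powers in section 12.2 are unsupported. Under the plan's main dmfs assumption the dmft SD is at least 1.47 in the control arm and about 2.1 pooled (2.0 under section 3.2's counting rule), so both 0.22 and 0.44 are excluded. Unadjusted power for 0.19 teeth is then about 0.15 at 100 per group and 0.19 at 141 at the most favourable SD, and 0.10 and 0.12 at the pooled floor. The result rests on 20 teeth with at most five surfaces each, on dmft being a count, and on SD 17.25 holding in both arms for the pooled figure. It does not extend to the dmfs SD of 11.2.

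A reader might go further and conclude that the trial is underpowered on dmft. The documents do not support that. For a 37% reduction, power could lie anywhere from about 0.49 to >0.99, because the plan does not fix the dmft mean and SD. What is shown is that the printed figures cannot stand beside the main dmfs assumption, and that a null dmft result should not be taken to exclude an effect of 0.19 teeth on the strength of them.

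**What to change.** - In section 12.2, remove the SDs of 0.22 and 0.44 and the three powers built on them.
- Restate dmft precision at 141 per group as the difference detectable with 80% power, which is 0.335 × SD: for illustration, 0.70 teeth at SD 2.1, 1.07 at SD 3.2 and 1.16 at SD 3.45. Alternatively, give power with mean, effect and SD taken from one population and one scale, consistent with the dmfs assumption.
- Use SDs at or above the pooled floor, label any floor as a lower bound and not an expected value, and state where the SD comes from.
- Settle one dmft definition across sections 3.2, 8.1 and 12.2.
- Qualify the sentence in section 12.2 that points to this calculation in support of the enrolment target.

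The cost is a recalculation, some rewording and one agreed definition. Enrolment is unchanged. The only downside is a less favourable stated power for the 0.19-tooth effect.
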